3.3 Outcome Measures

3.3.1. Primary Outcome Measure

Primary endpoint:

- a. Primary endpoint: The primary end point will be proportion of infusions with ≥ 1 IRR between the switching and comparator groups.
- b. Secondary IRR assessments:
 - a. We will also report the difference in the total number of IRRs after each infusion of ocrelizumab in the switching group compared to similar rituximab infusions in the comparator group.
 - b. The difference in proportion of patients with ≥ 1 IRR across any of their infusions between the switching and comparator groups
 - c. We will also compare the proportion of patients with an IRR following day 1 infusion versus the proportion of patients with an IRR at day 15 and month 6 infusions of ocrelizumab in the switching group.
 - d. The severity of IRRs will be assessed following each infusion of ocrelizumab in the switching and comparator group using the National Cancer Institute's Common Terminology for Adverse Events Scale.⁶ The frequency of each severity grade of IRR will be compared in a similar fashion.

Nursing staff at the University of Colorado's Outpatient Infusion Center will be responsible for classifying the severity of an IRR for each patient at the end of every ocrelizumab and rituximab infusion using the scale below. Nursing staff will be asked to record the highest grade of an IRR that they observed or intervened upon for each patient after completion of their infusion.

Severity of IRR:

Grade 0: No infusion reaction

Grade 1: Mild reaction (transient flushing or rash drug fever < 38 degrees C); infusion interruption not indicated; intervention not indicated

Grade 2: Requires therapy or infusion interruption but responds promptly to symptomatic treatment (e.g., antihistamines, NSAIDs, narcotics); prophylactic medications indicated for 24 hours.

Grade 3: Prolonged (i.e., not rapidly responsive to symptomatic medication and/or brief interruption of infusion); recurrence of symptoms following initial improvement; hospitalization indicated for other clinical sequelae (e.g., renal impairment, pulmonary infiltrates)

Grade 4: Life threatening consequences; urgent intervention indicated.

Grade 5: Death

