4.5.1 Assessments during Treatment

The following evaluations will be conducted during and post treatment:

Study Visits and Procedures Summary:

Study visits for the switching group include a) screening visit, b) first infusion of 300 mg of ocrelizumab (day 1 or T₀), c) 300 mg of ocrelizumab infusion on day 15 (T₁), d) 600 mg of ocrelizumab at 6 months (+/- 2 weeks) after day 1 (T₂) and, e) a research termination visit between month 12 and 18 - (+/- 2 weeks)(T₃). In some cases, screening procedures may be performed on the first infusion day rather than as a separate visit. The patient may continue on 600 mg of ocrelizumab or (if the patient prefers) 500mg rituximab at T₃, or 12 to 18 months after Day 1 (T₀). A month is defined as 28 days. Study visits for the comparator group include only standard of care infusion of rituximab, up to two infusions per patient, approximately 6 months apart. Research data on IRRs for the comparator group will be collected from the medical records.

A summary of all procedures for switching group is outlined under “Schedule of Events” in **Table 1** below. During the screening visit, patients will be consented for the study and receive both a medical and full neurological exam. Verification of their hepatitis B and C status including testing will be conducted if a patient has not been tested in the last two years. MS disease history and demographic information will also be collected. Patients will also receive an EDSS exam and take an online version of the PDDS (done as standard of care- on an iPad).

The Expanded Disability Status Scale (EDSS) is a commonly used assessment that allows clinicians to objectively measure changes in the disability status of MS patients using unbiased clinical raters.⁷ The **EDSS** provides a total score on a scale that ranges from 0 to 10. The first levels 1.0 to 4.5 refer to people with a high degree of ambulatory ability and the subsequent levels 5.0 to 9.5 refer to the loss of ambulatory ability. The range of main categories include (0) = *normal neurologic exam*; to (5) = *ambulatory without aid or rest for 200 meters; disability severe enough to impair full daily activities*; to (10) = *death due to MS*. In addition, it also provides seven subscale measurements called Functional System (FS) scores.

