4.9.4 Safety Analysis

The default analysis will be available case for all eligible participants on an intent to treat basis. Alpha = 0.05 for all tests. As in the OPERA I and II randomized clinical trials, the primary and secondary end points will be descriptively presented. Frequencies and percentages for the severity of IRR grades (Grades 0-5) will be presented for both study groups following each infusion time point and overall between groups. 95% confidence intervals for the proportions will be calculated. Differences in the distribution of IRR severity grades between independent samples (i.e. comparison between groups at a common time point) will be tested with the chi-square or Fisher's exact association test, and additionally with ordinal or multinomial logistic regression. If sample sizes are small among some levels of IRR severity grades, they may be collapsed or dichotomized (i.e. Grade 3 or higher, any reaction or no reaction, severe reaction or none as examples) and methods described for binary outcomes under secondary endpoints will be utilized. Dichotomization may be used to make analysis and presentation of results more manageable as well.

The primary endpoint will be the proportion of whether any IRR occurred (yes or no) per infusion cycle per patient in each study group. The secondary endpoints include the proportion per infusion per patient of severe infusion reaction (grade 3 or greater), the proportion of infusion reactions and severe infusion reaction per patient across all infusions, the proportion patients with anti-drug antibodies, and the proportion of patients with depleted B cells. The primary outcome, binary occurrence of IRR per infusion per patient, could be analyzed with logistic or relative risk models, with GEE (generalized estimating equations) and/or GLMM

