(generalized linear mixed models) methods to incorporate correlation on repeated infusions on a patient. The same method will apply to other longitudinal binary outcomes. Poisson or negative binomial models with exposure terms could calculate rates of IRR per infusion per patient as a counting process. Similar methods will be used to compare IRR rates between the switching group and OPERA I and II phase 3 clinical trials. The total number of IRRs experienced in each patient, will be analyzed with Poisson or negative binomial models. Paired T tests will be used to assess differences in specific cytokine markers between pre and post infusion at each infusion cycle. Patient reported outcomes will also be reported descriptively. Frequencies and proportions will be reported for adverse and serious events and loss to follow up

As contingency methodology, exact tests and confidence intervals for measures of association between categorical variables can be utilized when necessary, if the sample sizes for some of the cells are small. Transforms or rank based methods, such as Wilcoxon sign rank, can be used in place of the T-test if deviation for normality is severe. Otherwise the T-test is a robust test of mean differences for medium to large sample sizes. If matching leads to good balance between the treatment groups on the demographic and disease variables, including age, MS disease duration, and baseline PDDS score, then confounding will not be an issue and the proposed unadjusted tests should be adequate. Alternatively, if the demographic and disease variables are not balanced, then regression or propensity score methods will be used to adjust for potential confounding. Sensitivity analysis comparing unadjusted and adjusted results will be used to determine the extent of the confounding effect. Adjustment for covariates can sometimes improve the precision of the estimated treatment difference by reducing random noise in the outcome.

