5.2 Methods and Timing for Assessing and Recording Safety Variables

The investigator is responsible for ensuring that all AEs and SAEs that are observed or reported during the study, are collected and reported to the FDA, appropriate IRB(s), and Genentech, Inc. in accordance with CFR 312.32 (IND Safety Reports).

Adverse Event Reporting Period

The study period during which all AEs and SAEs must be reported begins after informed consent is obtained and initiation of study treatment or "initiation of any study procedures" and ends at T₃ which is 6 months after last dose of study medication. After this period, investigators should only report SAEs that are attributed to prior study treatment.

Assessment of Adverse Events

AEs and SAEs may be collected from medical record review, or elicited by asking non-directive questions at each study visit both before and after the infusion. Infusion-related AEs will be captured by the infusion nurses as well as self-reported by the patient as described in Outcome Measures. Patients will also be reminded to alert the study team about any concerning health issues between study visits. Each recorded AE or SAE will be described by its duration (i.e., start and end dates) and will include, and actions taken.

For all recorded AEs, a study investigator will make an assessment of seriousness, and causality. To ensure consistency of AE and SAE causality assessments, investigators should apply the following general guideline:

Yes

There is a plausible temporal relationship between the onset of the AE and administration of the ocrelizumab, and the AE cannot be readily explained by the subject's clinical state, intercurrent illness, or concomitant therapies; and/or the AE follows a known pattern of response to the ocrelizumab; and/or the AE abates or resolves upon discontinuation of the ocrelizumab or dose reduction and, if applicable, reappears upon re-challenge.

No

Evidence exists that the AE has an etiology other than the ocrelizumab (e.g., preexisting medical condition, underlying disease, intercurrent illness, or concomitant medication); and/or the AE has no plausible temporal relationship to ocrelizumab administration (e.g., event diagnosed 2 days after first dose of ocrelizumab).

Expected adverse events are those adverse events that are listed or characterized in the Package Insert or current Investigator Brochure.

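### The secondary count of IRRs has no like-for-like data source in the two groups, and its Poisson or negative binomial analysis lacks a robust variance and a required exposure term

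*Combined protocol and SAP*

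**What the plan says.** Section 3.3.1 makes the share of infusions with any IRR the primary endpoint. As a separate secondary assessment it adds: "We will also report the difference in the total number of IRRs after each infusion of ocrelizumab in the switching group", set against similar rituximab infusions in the comparator group. On data capture, the same section states: "Nursing staff will be asked to record the highest grade of an IRR that they observed or intervened upon", on a 0 to 5 scale, once the infusion is complete.

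Section 4.9.4 gives three relevant analyses:
- For the binary primary outcome, the data "could be analyzed with logistic or relative risk models, with GEE (generalized estimating equations) and/or GLMM" methods to handle repeated infusions.
- For rates, "Poisson or negative binomial models with exposure terms could calculate rates of IRR per infusion per patient as a counting process".
- For the count, "The total number of IRRs experienced in each patient, will be analyzed with Poisson or negative binomial models".

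Only the last is a firm commitment. It names neither a variance estimator nor an exposure term.

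There is a second data stream. Section 5.2 says "Infusion-related AEs will be captured by the infusion nurses as well as self-reported by the patient", and "Each recorded AE or SAE will be described by its duration", meaning start and end dates. For the other group, section 4.5.1 says "Research data on IRRs for the comparator group will be collected from the medical records", and that nurses use their standard-care scales. Section 4.2 concedes that IRRs are not collected by the same methods in the two groups.

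**The concern.** A count of reactions needs a rule for what one reaction is, and a record of each reaction made in the same way in both groups. The plan gives neither. The one instrument it describes for both groups, the nurse's grade, keeps only the worst reaction of each infusion. The grading scale also absorbs repeat events: symptoms that return after first settling are a Grade 3 criterion, not a second IRR.

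Two things are at stake. A result could be reported as a number of reactions when it is really a number of infusions with a reaction. Or the count could come from the adverse-event log in one group and the nurse grade in the other, which builds in a difference. In addition, a Poisson variance does not describe bounded 0/1 records repeated within patients, and the two groups have different planned numbers of infusions. The interval and p-value for this comparison would therefore not mean what they say.

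**Working it through.** **Inputs.** IRR risks of 14.3% (rituximab) and 34.3% (ocrelizumab), 95 patients per group and two-sided alpha 0.05 come from 4.9.6. Three ocrelizumab infusions and up to two rituximab infusions per patient come from 4.5.1. Within-patient correlation (rho) is in neither section, so I assume a range of 0 to 0.5.

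**1. The plan's own figure.** Pooled two-proportion test, mean risk 0.243:
- null SE = sqrt(2 × 0.243 × 0.757 / 95) = 0.0622
- alternative SE = sqrt((0.143 × 0.857 + 0.343 × 0.657) / 95) = 0.0605
- power = Φ((0.200 − 1.96 × 0.0622) / 0.0605) = 90%

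The stated 90% reproduces. It belongs to the binary endpoint; the plan states no power for the count.

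**2. What the record can yield.** One highest grade per infusion gives 0 (Grade 0) or 1 (Grade 1 or above). To illustrate what is lost, assume that reactions within an infusion are Poisson. The mean per infusion is then −ln(1 − p): 0.154 at 14.3% and 0.420 at 34.3%. The 0/1 record understates these by 7% and 18%. At equal 14.3% risk, a true count in one group set against 0/1 in the other gives 0.154 / 0.143 = 1.08 with no real difference.

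**3. One infusion per patient.** Poisson variance of a log rate is 1/(np); the true variance for 0/1 data is (1 − p)/(np). The SE ratio is 1/sqrt(1 − p) when both groups have the same risk:
- 14.3% in both groups: 1.08
- 34.3% in both groups: 1.23
- 14.3% v 34.3%: Poisson SE = sqrt(1/(95 × 0.143) + 1/(95 × 0.343)) = 0.323; true SE = sqrt(0.857/(95 × 0.143) + 0.657/(95 × 0.343)) = 0.289; ratio 1.12

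For the last case ln(0.343/0.143) = 0.875. Power of the Wald test is Φ(0.875/0.289 − 1.96) = 85.8% with the correct SE, and Φ((0.875 − 1.96 × 0.323)/0.289) = 79.9% with the Poisson SE. These are on the log-ratio scale and should not be set against the 90% above.

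**4. Patient totals, which is what 4.9.4 commits to.** With m infusions per patient the Poisson variance is 1/(nmp) and the true variance is (1 − p)(1 + (m − 1)rho)/(nmp). With 95 per group, m = 3 (ocrelizumab) and m = 2 (rituximab):

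| rho (assumed) | Poisson/true SE, 14.3% v 34.3% | Poisson/true SE, 14.3% in both | Actual alpha, 14.3% in both |
|---|---|---|---|
| 0 | 1.11 | 1.08 | 0.034 |
| 0.1 | 1.05 | 1.01 | 0.047 |
| 0.2 | 1.00 | 0.96 | 0.061 |
| 0.3 | 0.95 | 0.91 | 0.076 |
| 0.5 | 0.88 | 0.83 | 0.104 |

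Within one group the error changes sign at rho = p/((1 − p)(m − 1)): 0.17 for p = 0.143, m = 2; 0.26 for p = 0.343, m = 3; 0.08 for p = 0.143, m = 3. Negative binomial can add variance above these values but cannot remove it below them.

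Section 4.1 also allows up to 200 comparator patients for the 200 infusions, that is, one each. With 200 comparator and 100 switching patients the ratio runs from 1.11 to 1.02 (14.3% v 34.3%), and alpha from 0.034 to 0.074 (14.3% in both).

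**5. Simulation.** Beta-binomial data, 1,500 runs per setting, 14.3% in both groups, log-infusions offset, rho 0, 0.2 and 0.5. Type I error was 0.037, 0.055 and 0.102 with model-based Poisson SEs, and 0.060, 0.050 and 0.054 with robust SEs.

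**6. Exposure.** Without an offset, equal 14.3% risk gives expected totals of 3 × 0.143 = 0.429 and 2 × 0.143 = 0.286, a ratio of 1.5. With one infusion per comparator patient it would be 0.429 / 0.143 = 3.

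**The case against.** The strongest reply has four parts.

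- *The nurse's grade is a severity rule, not the only record.* Table 1 lists recording of IRRs and of adverse events as separate rows, and 5.2 gives each adverse event its own dates. This stands for the switching group, so a reader who infers that the count cannot be measured at all goes too far. It does not give a comparable count. The comparator has only standard-care grades and medical records, partly retrospective (3.1), and 5.3 prefers a diagnosis over individual signs and symptoms, so one reaction may be one entry in any case. Section 4.9.6 says the pilot captured both number and severity of IRRs, but it then describes highest-grade recording.
- *The total can be read as infusions with an IRR, which the grade supplies.* This is correct, but the endpoint is then the primary numerator under another name, and the plan should say so.
- *The plan already names GEE, relative risk models and exposure terms.* It does, but GEE is tied to binary outcomes and exposure terms are optional. Neither is attached to the sentence on patient totals.
- *Only a secondary assessment is touched.* This stands. Endpoints are to be presented descriptively, there is no family-wise error control, and 4.2 already limits between-group interpretation of IRRs.

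A reader might also infer that the intervals are always too wide, so that a real increase would be missed. The documents do not support that. It holds for a single infusion per patient, where Poisson is only an option. For patient totals the error can equally produce false positives.

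**Conclusion.** The point holds for one secondary assessment. The count of IRRs is undefined, and no like-for-like source for it is specified in the two groups. From the nurse grade it collapses to 0/1 per infusion.

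The stated model would give a model-based Poisson SE that is 8% to 23% too large with one infusion per patient. For patient totals at 14.3% v 34.3%, the Poisson SE is between about 11% above and 12% below the true value as rho goes from 0 to 0.5. The direction cannot be settled, because rho is an assumption. The spurious ratio of 1.5 needs no such assumption; it follows from 3 v 2 infusions if no offset is used.

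Nothing here weakens the primary endpoint: any IRR per infusion is obtainable from the grade in both groups, and the 90% power reproduces.

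**What to change.** In 3.3.1, replace the count with the number of infusions with an IRR (Grade 1 or above) out of infusions received, taken from the nurse grade in both groups. In 4.9.4, state one analysis for it: a binomial or relative-risk GEE on the infusion records, or a modified Poisson model with log(infusions received) as offset. Either should use robust variance clustered on patient; clustering on the patient identifier also covers people who contribute to both groups, which 4.1 permits.

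Once redefined, the endpoint nearly repeats the primary one, so deleting it is equally acceptable. Either route is a wording change in two sections and needs no new data.

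If a true number of reactions is wanted, the plan must define one IRR and record each reaction in the same way in both groups. That means new data collection, and it may not be recoverable for the retrospective rituximab infusions.

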3.3.2 Secondary Outcome Measures

- a. Anti-drug antibodies (ADAs): We will measure the number of patients who have treatment induced ADAs against rituximab and ocrelizumab prior to every ocrelizumab infusion (T_0 , T_1 , T_2) and at the research termination visit (T_3 =between month 12 and 18) in **ONLY** the switching group. This analysis will be performed by PPD Bio A Laboratories (in Richmond, VA) who will assess the anti-drug antibodies to ocrelizumab, and “QPS (Netherlands) who will assess the anti-drug antibodies to rituximab a single batch at end of study for the switching group.
- b. Treatment efficiency: We will measure B cell depletion before each ocrelizumab infusion (T_0 , T_1 and T_2), by the clinical laboratories (T cell and B cell panel) at the University of Colorado Hospital. We will measure the proportion of patients who are B cell depleted (CD-19+ and CD-20+) by the time of the next infusion and 6 to 12 months after the last infusion in the switching group.
- c. Cytokine profile: To better characterize infusion reactions and evaluate the contribution by either hypersensitivity reactions to ocrelizumab directly and/or by release of cytokines from dying CD20 positive cells, serum levels of cytokines will be evaluated. Cytokines will be measured using the MesoScale platform before the start of each ocrelizumab infusion, and after the infusion is completed (T_0, T_1, T_2, T_3). In addition, blood samples will be collected for those who experience a moderate to severe IRR to further examine cytokine profiles during an IRR. Plasma samples will be analyzed using the V-PLEX Human Biomarker 40-Plex Kit which assays for IFN- γ , IL-1 β , IL-2, IL-4, IL-6, IL-8, IL-10, IL-12p70, IL-13, TNF- α , GM-CSF, IL-5, IL-16, IL-7, IL-12/IL-23p40, IL-1 α , VEGF-A, IL-17A, IL-15, TNF- β , IL-8 (HA), MCP-1, MCP-4, Eotaxin, IP-10, MDC, Eotaxin-3, TARC, MIP-1 α , MIP-1 β , VEGF-C, VEGF-D, Tie-2, Flt-1/VEGFR-1, PIGF, FGF (basic), SAA, CRP, VCAM-1, ICAM-1 per manufacturer’s recommendation on a MesoScale SECTOR Imager 2400. This array of cytokines will provide information on the levels of cytokines being released during the infusion to determine if they are limited to those released by B cells. Patients will be categorized as either not having had an IRR (Grade 0), having had a mild

reaction (Grades 1-2), or a moderate/severe reaction (Grades 3-5). These patient groups will also be evaluated for difference before and after their infusions for changes in each of the above cytokines. These groups of patients will also be evaluated for the presence of antibodies to ocrelizumab as described above.

- d. Patient reported infusion tolerance: A short patient reported outcome scale describing the patient's experience to any IRR during the ocrelizumab infusion developed by the research team at RMMSC. will be administered by the study coordinators at the end of each infusion. Scale items will measure patient responses to their perception and experience of IRRs.

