Safety data from the Investigators Brochure on the OPERA I and II phase 3 trials comparing ocrelizumab to interferon β -1a on relapsing MS patients showed that IRRs were the most common adverse events experienced by patients treated with 600 mg of ocrelizumab.⁴ The percentage of patients experiencing IRRs was higher in the ocrelizumab group (relapsing forms of MS: 34.3%; primary progressive forms of MS 39.9%) compared with the interferon β -1a (active control) group who received placebo infusions (relapsing forms of MS: 9.7%; primary progressive forms of MS: 25.5%). The rate of IRRs was highest during the first infusion or Dose 1 (27.5% on Day 1; 4.71% on Day 15 of Dose 1) and decreased over time (13.7%; 9.6% and 7.8% following Dose 2, 3, and 4 respectively) for the ocrelizumab treated group. Comparatively, interferon β -1a users experienced 6.5% of IRRs on Day 1, 2.58% on Day 15, \leq 2.00% after doses 2, 3 and 4 respectively. The reported IRRs were primarily mild-to-moderate in severity (Grades 1 and 2). Serious IRRs occurred in 0.1% and 1.0% respectively of relapsing and progressive patients and treated with ocrelizumab.

Clinical data describing the efficacy and tolerability profile of rituximab and ocrelizumab has utilized populations with different prior treatment characteristics. In the phase 2 HERMES trials, a majority (78.5%) of rituximab patients had been **previously been treated** with a disease modifying therapy in the last 2 years.³ In contrast, the OPERA I and II phase 3 clinical trials, a majority of ocrelizumab

patients (72.9% in OPERA I and 73.8% in OPERA II) represented a **treatment naïve population**.⁴ Examining IRRs in patients who have switched from rituximab to ocrelizumab versus those continuing on rituximab will evaluate the magnitude of the IRRs and subsequent tolerability of ocrelizumab in a real world population of MS patients previously been exposed to rituximab.

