For the comparator group, they may be approached to gauge interest in the study via telephone. If they are interested, the consent can be sent to them. These patients will be given the following options: 1) complete consent process orally over the phone with coordinator (and a treating physician if patient desires), sign and date the consent form and send back to coordinator via mail, fax, or email, 2) complete consent process with coordinator (and a treating physician if patient desires) in person at their next scheduled rituximab infusion. In either case, data collection will not begin until written consent is obtained. Following each rituximab infusion, nursing staff will record IRR using scales as part of standard care.

As required by the University of Colorado's Institutional Review Board, an independent Data and Safety Monitoring Board (DSMB) will meet at initiation of the study and every 6 months thereafter until the end of the study.

Table 1. Schedule of Events (for switching group)

Data Collection Event	Screening Visit^a	Day 1 (T₀) 300 mg of OCR^a	Day 15 (T₁) 300 mg of OCR)	6 months (T₂) (600 mg of OCR)	12 -18 months research termination visit (T₃)
Informed Consent	X				
Medical Exam	X				
Physical Exam	X				
Demographics and MS Disease History	X				
Concomitant Meds	X	X	X	X	X*
Vital Signs		X	X	X	X
Hepatitis B and C evaluation confirmed	X				
EDSS	X				
PDDS	X				X*
Pre-infusion blood draw:					
Lab: CBC, CMP		X		X	X
Lab: B and T cell subsets by flow cytometry		X		X	X
Lab: immunoglobulin panel		X		X	X
Lab: Binding antibodies		X		X	X
Pre and post-infusion blood draw and during moderate/severe reactions:					
Lab: Cytokine levels		X	X	X	
Administration of Ocrelizumab		X	X	X	
Pre-medication of 100 mg of methylprednisolone		X	X	X	
Nurses record IRRs		X	X	X	
Nurses/Study Coordinator record AE		X	X	X	X*
Patient self-report of IRRs		X	X	X	

* may be completed over the phone

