4.9.6 Determination of Sample Size

The sample size will be a convenience sample. It is anticipated a minimum of 100 patients will qualify for each cohort (200 total) resulting in studying 300 infusions with ocrelizumab and 200 infusions with rituximab. This is an observational study not designed to demonstrate superiority of ocrelizumab over rituximab in efficacy but instead indicate the magnitude of the relative tolerability and immunogenicity. The primary endpoint is the difference in the percentage of IRRs between the two study groups. In addition, both study groups will include treatment experienced patients on rituximab who have experienced a minimum of two infusions and either continue to stay on rituximab or switch to ocrelizumab.

To estimate study power with the proposed sample size of 100 infusions in each group, we conducted a chart review of 50 patients at the Rocky Mountain MS Center who are currently taking rituximab and examined their IRRs using the proposed IRR grading scale (see section 3.3.1) from Grade 0-5. The number and severity of IRRs were captured following their third rituximab infusion. The highest grade of an IRR that occurred during the infusion was recorded. Our pilot data revealed that following the third rituximab infusion, 14.3% of patients had an IRR of which 85.71% were Grade 0, 12.24% were grade 2 and 2.05% were Grade 3. Hauser et al., found that following the second infusion of rituximab in patients, the majority of whom (60%) were not taking a DMT for 6 months prior to initiating rituximab only 20.3% experienced in an IRR.³

Using IRR estimates from our pilot data and establishing a clinically meaningful difference of 20% increase in IRRs, we conducted the following power analysis for a sample of 95 patients (assuming a 5% attrition rate after recruiting 100 patients in each study group). An IRR proportion for ocrelizumab users at 34.3% compared with 14.3% for rituximab (obtained from our pilot data) for a two sided (alpha = 0.05) two sample proportion test for the null hypothesis of no difference between rituximab and ocrelizumab in proportion of IRRs would result in 90% power for 95 patients per group.

In response to the FDA IND letter, “the power analysis in Section 4.9.6 of the protocol appears to compare the infusion-related reaction (IRR) rate at the third rituximab infusion (14.3%) to that of the first infusion of OCR (34.3%). Because

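### The cytokine comparison groups patients by IRR category although cytokines and IRR grade are both recorded at each infusion; if the category means any IRR, reaction-free infusions enter the IRR groups and weaken the contrast

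*Combined protocol and SAP*

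**What the plan says.** Section 3.3.2c sets the cytokine sampling by infusion: "Cytokines will be measured using the MesoScale platform before the start of each ocrelizumab infusion, and after the infusion is completed". Table 1 in section 4.5.1 marks cytokine levels at T0, T1 and T2 under the row "Pre and post-infusion blood draw and during moderate/severe reactions". Section 3.3.1 also sets IRR grading by infusion: nurses are to "record the highest grade of an IRR that they observed or intervened upon for each patient after completion of their infusion".

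The comparison in 3.3.2c uses a different unit: "Patients will be categorized as either not having had an IRR (Grade 0), having had a mild". Grades 1-2 form the mild class, and a third class for moderate/severe reactions takes Grades 3-5. The cytokine change is then tied to those classes: "These patient groups will also be evaluated for difference before and after their infusions for changes in each of the above cytokines". The same patient groups are then used for the presence of antibodies to ocrelizumab.

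Section 4.9.4 has one sentence on cytokine analysis: "Paired T tests will be used to assess differences in specific cytokine markers between pre and post infusion at each infusion cycle". It mentions no IRR category, no test between categories and no term for repeated infusions in a patient. The GEE and GLMM methods in that section are tied to the primary outcome and other longitudinal binary outcomes, and cytokine levels are continuous.

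**The concern.** Cytokine release, if it contributes to a reaction, should appear at the infusion where the reaction occurred. A patient with Grade 2 at T0 and Grade 0 at T1 and T2 has one pre/post pair from a reacting infusion and two from reaction-free infusions. If that patient carries a single category, all three pairs sit in the mild-reaction group, and the difference from the Grade 0 group is pulled toward zero.

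The purpose of this outcome is to learn whether cytokine release contributes to IRRs. The Introduction says the answer may bear on future premedication practice, so a contrast biased toward no association could lead to the hypothesis being dismissed wrongly. A patient-level grouping also leaves unused the comparison of reacting with non-reacting infusions in the same patient, which is free of stable differences between patients.

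**Working it through.** **The plan's own figure.** None is given for the cytokine comparison. The only power statement (section 4.9.6: 34.3% v 14.3%, 95 per group, two-sided 0.05) reproduces at 90.1% and is not touched by this point.

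**Inputs**
- Three infusions per switching patient: section 4.9.6 plans "300 infusions with ocrelizumab and 200 infusions with rituximab" with 100 switching patients.
- OPERA rates from the Introduction: "The rate of IRRs was highest during the first infusion or Dose 1 (27.5% on Day 1; 4.71% on Day 15 of Dose 1", and 13.7% after Dose 2, taken here as the month 6 infusion.
- OPERA share of relapsing patients with any IRR (Introduction): 34.3%.
- Assumptions: these rates apply to switchers, and the category means at least one IRR over the three infusions. Grades 1-2 and 3-5 are merged into one IRR group for the arithmetic.

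**Step 1, reacting infusions per 100 patients.** 27.5 + 4.71 + 13.7 = 45.91.

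**Step 2, range for patients who ever react.** The share cannot be below the Day 1 rate, 27.5%. It should not exceed 34.3%, which covers the whole OPERA treatment period, with IRRs reported through Dose 4.

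**Step 3, all three infusions pooled.** Reacting share among IRR patients' infusions = 45.91 / (3 × ever-reacting patients per 100).

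| Ever react | Infusions in IRR patients | Reacting | Reaction-free |
|---|---|---|---|
| 27.5% | 82.5 | 45.91/82.5 = 55.6% | 44.4% |
| 34.3% | 102.9 | 45.91/102.9 = 44.6% | 55.4% |

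**Step 4, by cycle.** Section 4.9.4 works by cycle, so the same category can be applied there. Share of IRR patients who react at that infusion = cycle rate / ever-reacting share.

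| Cycle | 34.3% ever react | 27.5% ever react |
|---|---|---|
| Day 1 (T0) | 27.5/34.3 = 80% | 100% |
| Day 15 (T1) | 4.71/34.3 = 14% | 17% |
| Month 6 (T2) | 13.7/34.3 = 40% | 50% |

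**Step 5, effect on the contrast.** Let δ be the difference in mean change between a reacting and a reaction-free infusion. If reaction-free infusions in reactors have the same mean change as infusions in non-reactors, the expected group difference is (reacting share) × δ. Pooled, 45% to 56% of δ remains. By cycle with 34.3% ever reacting, 80%, 14% and 40% remains.

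**Step 6, if OPERA rates do not transfer.** Take instead the pilot rate of 14.3% at each of three infusions, with beta-binomial correlation ρ within patients (an assumption, since the plan gives no value). The reaction-free share is 61% at ρ = 0, 50% at ρ = 0.3 and 41% at ρ = 0.5. At 34.3% per infusion it is 52%, 42% and 34%. The size therefore depends on the rates and on how far reactions recur in the same patients.

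**The case against.** The strongest reply is that the text never says ever, any or worst grade. Elsewhere the protocol speaks of patients when it means status at one infusion: section 3.3.1 compares the proportion of patients with an IRR after Day 1 with Day 15 and month 6. Together with the per-cycle t tests in 4.9.4, the category could be the same-infusion grade, which causes no dilution. This stands as a possible reading. It does not settle the matter, because 3.3.2c pairs patient groups with infusions in the plural, reuses those groups for a patient-level antibody comparison, and gives no rule for mixed grades.

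A reader might infer that a true cytokine signal is simply halved. The documents do not support that. It requires the any-IRR reading, pooling over cycles (which no section specifies) and OPERA rates in switchers. OPERA patients were mostly treatment-naive (72.9% and 73.8%), while switchers have had at least two rituximab doses. By cycle the loss is uneven, and most of the contrast survives at Day 1.

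A reader might also take independent reactions, giving 1 − 0.725 × 0.9529 × 0.863 = 40.4% ever reacting and 38% of the contrast kept, or no overlap, giving 45.9% and 33%. On the OPERA rates both exceed the 34.3% overall share, so neither belongs in the range.

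The draw during a moderate/severe reaction is tied to the reacting infusion and is not diluted. Its cover is limited, though. If moderate/severe there means Grades 3-5, as in the 3.3.2c grouping, most reactions would have no such sample: in the pilot, Grade 2 made up 12.24 of the 14.29 percentage points of reactions (86%).

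**Conclusion.** The point holds in a conditional form. Section 3.3.2c defines the comparison groups by patient while both variables are recorded by infusion, and 4.9.4 supplies no between-category analysis that would resolve this. Under an any-IRR category with OPERA rates and 27.5% to 34.3% ever reacting, about 44% to 55% of pooled IRR-group infusions would be reaction-free. By cycle with 34.3% ever reacting, about 20%, 86% and 60% would be reaction-free at Day 1, Day 15 and month 6. The bias is toward no association, provided reaction-free infusions in reactors resemble those in non-reactors.

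The documents do not establish that the sponsor intends an any-IRR category, so the loss is a risk of the wording and not a certainty. Sections 2.2 and 3.3.2 list the cytokine outcome as secondary, and section 3.1 lists it as exploratory. The primary endpoint and its power are unaffected. This is a cheap improvement.

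**What to change.** In 3.3.2c and 4.9.4, state that the pre-to-post cytokine change at each infusion is compared by the IRR grade of that same infusion. Use a mixed model or GEE with a within-patient term and an infusion-cycle term (T0, T1, T2). The cycle term matters because on OPERA rates 27.5/45.91 = 60% of reactions fall at Day 1 and the T2 dose differs from T0 and T1, so grade and cycle would otherwise be confounded.

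Keep the patient-level grouping for the antibody comparison, where it is reasonable, and as a descriptive cytokine summary with its rule for mixed grades written down. If same-infusion grading was always intended, the same edit is needed, because the plan does not say so.

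The cost is wording in two sections and slightly more modelling work. No new samples, visits or data items are required, since the grade is already recorded at each infusion.
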